3.2 Outcome variables

3.2.1 Primary Outcome Variables

The primary outcome variables which address the safety and tolerability of AZD7648 monotherapy or with a specific combination partner are described in Section 3 of the Clinical Study Protocol.

3.2.1.1 Duration of Exposure

Extent of exposure for AZD7648 and PLD will be defined in terms of the number of days the treatment is received.

Exposure (i.e., duration of treatment) will be defined as follows:

1. Total treatment duration (if IP not discontinued after the last dose > 0 mg) = (min (last dose date where dose > 0 mg + Z, date of death, date of DCO) – date of first dose +1).

2. Total treatment duration (if IP discontinued after the last dose > 0 mg) = (min (last dose date where dose > 0 mg, date of death, date of DCO) – date of first dose +1).
 - If the planned schedule is continuous (28 days) intake (core module), Z=0
 - If the planned schedule is to take continuously for the first 7 days in the cycle, Z=21

The planned schedule of PLD dosing is once at the start of each cycle, Z=27

Similar imputation rule will be used for counting the duration of dose interruption.

3. Actual treatment duration = total treatment duration, excluding dose interruptions not in accordance with the protocol, and any planned no dose periods.

Exposure will also be measured by the number of cycles received. A cycle corresponds to a period of 28 days. If a cycle is prolonged due to toxicity, this should still be counted as one cycle. A cycle will be counted if treatment is started even if the full dose is not delivered.

Where total exposure will be calculated as above, and a dose interruption is defined as any length of time (number of days) where the patient has not taken any of the planned daily dose.

Missed or forgotten doses

Missed and forgotten doses should be recorded on the dosing page as a dose interruption with the reason recorded as “Patient forgot to take dose”. These missed or forgotten doses will not be included as dose interruptions in the summary tables, but the information will appear in the listing for dosing. However, these missed and forgotten doses will be considered in the derivation of actual exposure.

Patients who permanently discontinue during a dose interruption

If a patient permanently discontinues study treatment during a dose interruption, then the date of last recorded administration of study medication will be used in the programming.

3.2.1.2 Relative dose intensity

Dose intensity of AZD7648 and PLD will be addressed by considering relative dose intensity (RDI). Relative dose intensity (RDI) is the percentage of the actual dose delivered relative to the intended dose through to treatment discontinuation. Relative dose intensity (RDI) will be defined as follows:

$$\text{RDI (\%)} = 100 * d/D,$$

where

d the actual cumulative dose delivered up to the actual last day of dosing based on the study treatment schedule and

D is the intended cumulative dose up to the actual last day of dosing based on the study treatment schedule. D is the total dose that would be delivered, if there were no modification to dose or schedule.

If a participant permanently discontinues study treatment, then the date of last administration of study medication recorded on eCRF will be used to program the RDI. If a participant permanently discontinues study treatment during a treatment interruption, then the date of last administration of study medication recorded on DOSEDISC of the eCRF will be used to program the RDI.

The actual treatment duration, total treatment duration and RDI will be summarised. Exposure swimmer plot will be produced, with a line presented for each participant to display relevant exposure and disposition details.

3.2.1.3 Dose limiting toxicities (DLTs) and patients evaluable for DLTs

A patient will be defined as evaluable if they have completed the DLT evaluation period with sufficient dosing, at least 75% of the total amount of planned dose of AZD7648 (and PLD for combination module 1). Additionally, patients who have a DLT are considered evaluable. Patients who withdraw from the study prior to completion of the first 28 day safety observation period for reasons other than a DLT will not be considered evaluable.

At each SRC meeting, the patients in the current dose escalation cohort are reviewed by the SRC, the SRC will agree on the patients who are evaluable or have a DLT following Section 6.1.3 of the CSP. The evaluable patients will be used by the SRC to inform the next dose decision.

See Section 6.1.3 of the Clinical Study Protocol for the definition of a DLT. For reporting purposes, the DLTs and the list of DLT evaluable patients are as approved and documented at the Safety Review Committee meetings.

3.2.1.4 Adverse Events

Adverse events (AEs) and serious adverse events (SAEs) will be collected throughout the study, from date of informed consent until 28 days after the last dose of study treatment. Events will be defined as treatment emergent if they onset, or worsen (by investigator report of a change in intensity), during the

treatment period starting from the first dose on cycle 0, day 1 or during the 28-day safety follow-up period. Any events in this period that occur after a patient has received further therapy for cancer (following discontinuation of study treatment) will be flagged in the data listings. The latest version of MedDRA will be used to code the AEs. AEs will be graded according to the National Cancer Institute of Common Terminology Criteria for AEs (CTCAE version 5.0 or higher).

In general, all AE summary tables include only treatment emergent AEs. AEs occurring prior to dosing or starting more than 28 days after discontinuation of study drug will be flagged in listings and will not be included in any summaries.

All reported AEs will be listed along with the actual treatment received at the time of onset, date of onset, date of resolution (if AE is resolved), investigator's assessment of CTCAE grade, relationship to study treatment, action taken and outcome. Frequencies and percentages of patients reporting each preferred term will be presented (i.e., multiple events per patient will not be accounted for, except for event level summaries).

Summaries of adverse events (the number and percentage of patients by treatment) by MedDRA System Organ Class (SOC) and Preferred Term (PT) will include but are not limited to:

- All AEs.
- All AEs possibly related to study treatment.
- AEs of CTCAE grade 3 or higher.
- AEs of CTCAE grade 3 or higher, possibly related to treatment.
- AEs with outcome of death.
- All SAEs.
- All SAEs possibly related to study treatment.
- AEs leading to discontinuation of treatment.
- AEs leading to discontinuation of treatment, possibly related to treatment.
- SAEs leading to discontinuation of treatment.
- SAEs leading to discontinuation of treatment, possibly related to treatment.

Other significant adverse events (OAE)

No OAEs are planned to be defined for this study.

3.2.1.5 Prior/Concomitant Medications and procedures

The latest version of World Health Organization Drug Dictionary (WHODD) will be used to code any medications and the version used will be clearly stated as footnote in the summary tables. Allowed concomitant medication will be summarised by anatomical therapeutic chemical (ATC) level classification, by generic term. Concomitant procedures will be summarised by system organ class, by MedRA preferred term.

3.2.1.6 Vital Signs Changes

Changes from baseline in vital signs to each post-baseline assessment will be calculated. Absolute values, changes from baseline and percentage change from baseline will be summarised by module, by part, by cohort and visit.

There will be no imputation for missing values. Observed values and changes from baseline will be compared to the relevant AstraZeneca defined reference ranges for vital signs (see [Table 5: AstraZeneca defined reference ranges for vital signs variables](#) and clinically important change criteria and all values (observed and change) falling outside the reference ranges will be flagged in the listings.

Table 5: AstraZeneca defined reference ranges for vital signs variables

Vital sign (unit)	Outside AZ defined reference range lower limit if	Outside AZ defined reference range upper limit if	Treatment emergent decrease if	Treatment emergent increase if
SBP (mmHg)	<100	>160	<-30	>30
DBP (mmHg)	<60	>100	<-15	>15
Pulse	<40	>100	<-20	>20
Height (cm)	<140	>220		
Weight (kg)	<40	>200		

SBP- systolic blood pressure; DBP-diastolic blood pressure.
mmHg-millimeter of mercury; cm-centimeter; kg-kilogram.

3.2.1.7 Laboratory Data

All laboratory results collected will be listed.

Summaries for safety laboratory will only include the parameters specified in [Table 6](#).

All values will be classified as low (below range), normal (within range), or high (above range) based on local laboratory reference ranges. Results will be converted to standard units and graded with CTCAE version 5.0. A shift table from baseline to maximum value will be summarised for urinalysis variables. Maximum post-baseline CTC grade will also be calculated.

If the same parameter is found as measured in serum and in plasma, then the summaries will not distinguish between them (e.g. values from plasma albumin and serum albumin will be summarised under albumin). If the same parameter is found as measured in serum and in plasma within the same patient, which would be a rare case, then the change from baseline will only be calculated for those post-baseline values using the same source, i.e., only within plasma or serum. If one patient has multiple toxicity grades, because they are derived separately from serum and plasma then the maximum value of the two will be considered.

For all continuous laboratory assessments, absolute value, change from baseline and percentage change from baseline will be summarised using descriptive statistics at each scheduled assessment time by actual treatment group.

For clinical chemistry and haematology, shift tables will present movements from baseline to worst value on-treatment (defined from start of treatment to biopsy day) according to reference range classification. CTCAE grade changes from baseline to on-treatment will also be provided. Corresponding shift tables (“Negative”, “Trace”, “Positive”, “0”, “+”, “++”, “+++”) will be produced for urinalysis. In addition, the number of patients with ≥ 2 CTCAE grade changes and CTCAE grade changes to 3 or 4 will be summarised by actual treatment group for clinical chemistry and haematology parameters.

Plots for both maximum post-baseline alanine transaminase (ALT) and aspartate transaminase (AST) versus the maximum post-baseline total bilirubin (expressed as multiples of their upper limit of normal [ULN] reference range) will be produced with reference lines at 3 x ULN for ALT and AST and 2 x ULN for total bilirubin. Spaghetti plots of absolute values and change from baseline values for all haematology and clinical chemistry parameters will also be presented.

Liver biochemistry test results over time for patients who show elevated ALT or AST (≥ 3 x ULN) and elevated bilirubin (≥ 2 x ULN) (elevated results do not need to be present at the same visit) or ALT or AST of ≥ 5 x ULN, will be tabulated and plotted.

Table 6: Laboratory safety variables

Haematology/Haemostasis (whole blood)	Clinical Chemistry (serum or plasma)
B-Haemoglobin (Hb)	S/P-Creatinine

B-Leukocyte count	S/P-Bilirubin, total
B-Leukocyte differential count (absolute count) ^[a]	S/P-Alkaline phosphatase
B-Platelet count	S/P-Aspartate transaminase
B-Reticulocyte count	S/P-Alanine transaminase
Coagulation	S/P-Albumin
INR	S/P-Potassium
Activated Partial Thromboplastin Time (APTT)	S/P-Calcium, total
Urinalysis (dipstick)	S/P-Sodium
U-Hb/Erythrocytes/Blood	S/P-Urea nitrogen
U-Protein/Albumin	S/P-Phosphate
U-Glucose	S/P-Magnesium
	S/P-Gamma-glutamyl transferase
	S/P-Total protein
	Thyroid stimulating hormone (TSH) ^[b]
	C-reactive protein (CRP) ^[b]
	Tumour markers

[a] If absolute differentials are not available, % differentials (differential includes neutrophils, lymphocytes, monocytes, basophils, eosinophils) will be provided.

[b] TSH to be measured at baseline and every 3 cycles. CRP to be collected at baseline, then on Day 1 from Cycle 1. Urinalysis at Cycle 0, Cycle 0+1 and Day 1 of each cycle. Tumour markers (if relevant) to be measured at baseline and on Day 1 of every cycle from Cycle 1 (only if elevated at baseline).

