^b Weekly visit may be omitted if Visit Y is within 2 days of weekly visit.

Visit Y is only utilised if the dosing schedule is intermittent. Visit Y represents the last AZD7648 dosing day in the first block of AZD7648 treatment in a cycle eg, CCI

^d There are no visit windows in Cycle 0 and Cycle 1.

^e With the patient's consent, as part of the medical history, any available information on known tumour gene mutations will be collected.

^f Targeted physical examinations only required if clinically indicated (indication should be stated).

^g Vital signs then ECG measurements will be collected prior to PK blood draws at all PK sample timepoints. Timepoints may be modified based on initial data obtained.

- ^h Serious adverse events (SAEs) only to be collected between AZD7648 discontinuation and disease progression
- ⁱ Women of child-bearing potential must have a negative urine or serum pregnancy test at screening, a confirmatory test before treatment on Day 1 (Cycle 0 or Cycle 1), at regular intervals during treatment and at AZD7648 discontinuation. If results are positive, the patient is ineligible/must be discontinued from study treatment and not discontinued from the study. The patient will continue to be followed up according to the study protocol.
- ^j TSH to be measured at baseline and every 3 cycles. CRP to be collected at baseline, then on Day 1 from Cycle 1. Urinalysis at Cycle 0, Cycle 0+1 and Day 1 of each cycle. Tumour markers (if relevant) to be measured at baseline and on Day 1 of every cycle from Cycle 1 (only if elevated at baseline).
- ^k Provision of archival tumour samples is mandatory for all patients. The samples may be submitted retrospectively.
- ¹ Fresh biopsy samples are encouraged in Part A (particularly in patients with accessible tumours) and are mandatory for patients enrolled into Part A PD expansion cohorts (or a PD subgroup of an efficacy expansion cohort). Serial biopsies will be collected during screening, on treatment (any time in Cycle 1 between Day 3 and Day 8 [or Y] 2 to 8 hours [h] post AZD7648 dosing), and on progression.

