^a 1 cycle = 28 days. Cycles repeat on a continuous basis with no interval between cycles.

^b Weekly visit may be omitted if Visit Y is within 2 days of weekly visit.

• Visit Y is only utilised if the dosing schedule is intermittent. Visit Y represents the last AZD7648 dosing day in the first block of AZD7648 treatment in a cycle eg, CCI

^d There are no visit windows in Cycle 0 and Cycle 1.

- e With the patient's consent, as part of the medical history, any available information on known tumour gene mutations will be collected.
- f Targeted physical examinations only required if clinically indicated (indication should be stated).
- ^g Vital signs then ECG measurements will be collected prior to PK blood draws at all PK sample timepoints. Timepoints may be modified based on the initial data obtained.
- ^h Serious adverse events (SAEs) only to be collected between AZD7648 discontinuation and disease progression.
- ⁱ Women of child-bearing potential must have a negative urine or serum pregnancy test at screening, a confirmatory test before treatment on Day 1 (Cycle 0 or Cycle 1), at regular intervals during treatment and at AZD7648 discontinuation. If results are positive, the patient is ineligible/must be discontinued from the study treatment and not discontinued from the study. The patient will continue to be followed up according to the study protocol.
- ^j TSH to be measured at baseline and every 3 cycles. CRP to be collected at baseline, then on Day 1 from Cycle 1. Urinalysis at Cycle 0, Cycle 0 + 1 and Day 1 of each cycle. Tumour markers (if relevant) to be measured at baseline and on Day 1 of every cycle from Cycle 1 (only if elevated at baseline).
- k LVEF assessment (ECHO or MUltiGated Angiography [MUGA]) and review must occur at screening and prior to dosing at Cycle 4 Day 1 and Cycle 7 Day 1 (-7 day window).
- ¹ Provision of archival tumour samples are mandatory for all patients. The samples may be submitted retrospectively.
- ^m Fresh biopsy samples are encouraged in Part A (particularly in patients with accessible tumours) and are mandatory for patients enrolled into Part A optional PD expansion cohorts (or a PD subgroup of an optional efficacy expansion cohort). Serial biopsies will be collected during screening, on treatment (any time in Cycle 1 between Days 3 and Visit Y 2 to 8 hours [h] post AZD7648 dosing), and on progression.

		-	-	 	
n	CCI				
0	I CCI				

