1.2 List of modules

The following modules for the study are included within this SAP.

Core Module: AZD7648 Monotherapy. Part A, dose escalation

Combination Module 1: AZD7648 + PLD. Part A, dose escalation.

For the endpoints included in the safety, efficacy and exploratory objectives, see [Table 1](#).

Table 1 : Study objectives and endpoints

Primary objective (Safety):	Endpoint/Variable:
To investigate the safety and tolerability of AZD7648 when given orally to patients with advanced malignancies, as monotherapy and in combination with anti-cancer agents, and define	
 • Adverse events (AEs)/serious adverse events (SAEs) • Dose limiting toxicities (DLTs) • Physical examination

the doses and schedules for further clinical evaluation.
	
 • Eastern Cooperative Oncology Group performance status (ECOG PS) • Vital signs • Electrocardiogram (ECG) and Echocardiogram (ECHO; applicable for Combination Module 1 only) • Laboratory data

Secondary objectives:
	
Endpoint/Variable:

To characterise the PK of AZD7648, following a single dose and at steady state after multiple dosing, when given orally as monotherapy and in combination with anti-cancer agents.
	
 • Area under the curve to infinity (AUC_{inf}) and/or AUC_{last} after a single dose and AUC_∞ after multiple doses. • Maximum plasma concentration (C_{max}) after single and multiple doses. • Time to reach maximum plasma concentration (t_{max}) • Minimum plasma concentration at steady state (C_{min}) • Half-life (t_{1/2λz}) • Accumulation ratio (R_{ac}) • Dose proportionality (TCP) • AUC_{last} and C_{max} ratio for food effect (applicable for food effect cohort only in the Core module expansion phase) • Other PK parameters may also be estimated

^[a]To understand the cytochrome P450 3A4 (CYP3A4) induction potential of AZD7648
	
Post-dose to pre-dose 4β-hydroxy cholesterol ratio (only for AZD7648 Core Module)

To obtain a preliminary assessment of anti-tumour activity of AZD7648 as monotherapy and in combination with anti-cancer agents
	
Radiological response evaluated using response evaluation criteria in solid tumours (RECIST 1.1)
 
 • Percentage best change in target lesion (TL)

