The reference date for all assessments except for tumour assessments, will be the start of the study treatment in cycle 0 (i.e., cycle 0, day 1). There is no study day 0 for this study. Date of cycle 1, day 1 dosing will be considered as the start date for the calculation of efficacy endpoints (tumour response, PFS), which follows CSP visit window starting from cycle 1, day 1. The study day will be displayed in the data listings. If an event starts before the reference start date, the study day displayed on the listing will be negative.

Time Windows

Time windows will need defining for any presentations that summarise values by visit.

Given the washout period between Cycle 0 and Cycle 1 can vary between patients (3-7 days per CSP) and therefore study day of Cycle 1 Day 1 onwards will vary, for the purposes of windowing assessments the study day of visits from Cycle 1 Day 1 onwards will be adjusted in order to allow the same window to be applied across patients. This will not impact on study day displayed in listings and will be used only by programming as an intermediate step to assign analysis visits. The amount to adjust the study day by will be derived assuming the planned day for Cycle 1 Day 1 is day 8 for all patients:

Adjustment (days) = 8 – actual Cycle 1 Day 1 study day

Study day for all safety assessments from Cycle 1 Day 1 onwards will be adjusted by this amount when assigning assessments to analysis visits. Actual, unadjusted study day will be presented in listings.

The following conventions should apply:

- Inclusion within the time window should be based on the actual date and not the intended date of the visit.
- The visit window following baseline will be constructed as per [Table 4](#) for the safety assessments
- For summaries showing the maximum or minimum values, the maximum/minimum value recorded on treatment will be used (regardless of where it falls in an interval).
- Listings should display all values contributing to a time point for a patient.
- Often the most meaningful summaries focus on extreme values rather than summaries at each visit but if summaries over time are felt to be required:
- For visit based summaries

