 - If there is more than one value per patient within a time window then the closest value to the scheduled visit date should be summarised, or the earlier, in the event the values are equidistant from the nominal visit date. The listings should highlight the value for the patient that contributed to the summary table, wherever feasible. Note: in summaries of extreme values, all post baseline values collected are used including those collected at unscheduled visits regardless of whether or not the value is closest to the scheduled visit date
- For summaries at a patient level, all values should be included, regardless of whether they appear in a corresponding visit-based summary, when deriving a patient level statistic such as a maximum.

Table 4: Visit windowing (safety analysis)

Cycle	Target Day	Analysis visit	Analysis Visit Window
	screening	Baseline	Day -28 to Cycle 0 Day 1 (pre-dose)
C0	Day 1 (pre-dose)		No analysis visit window: First day of intake of AZD7648

C0	Day 2	Cycle 0 Day 2	C0D1 + 1 day
C0	Day 3	Cycle 0 Day 3	C0D1 + 2 days
C0	Day 4	Cycle 0 Day 4	C0D1 + 3 days
C1	Day 1	Cycle 1 Day 1	No analysis visit window: Monotherapy: First day of restart of AZD7648 after C0 Combinations: Day 1 of associated anticancer agent or first day of restart of AZD7648 after C0 whichever comes first
C1	Day Y	Cycle 1 Day Y	If Y=3 then Day 2 to Day 4 If Y=7 then Day 2 to Day 7
C1	Day 8	Cycle 1 Day 8	^a Last day of previous interval + 1 day to Day 11
C1	Day 15	Cycle 1 Day 15	Day 12 to Day 18
C1	Day 22	Cycle 1 Day 22	Day 19 to C2D1 – 2 days if following cycle Otherwise Day 19 to C1D1+26 days (last cycle)
C2	Day 1	Cycle 2 Day 1	From: Monotherapy: C1D1 + 28 – 1 day or (first day of intake of AZD7648 after C1D1+28) - 1 day; if AZD7648 is off on C1D1+28-1 day. Combinations: (Day 1 of associated anticancer agent for C2 or C1D1 + 28) – 1 day; if associated anticancer agent stopped;

			
or
 
(first day of intake of associated anticancer agent after C1D1+28) – 1 day; if associated anticancer agent is off since C1D1+28-1 day
 
To:
 
Monotherapy: C1D1 + 28 + 1 day
 
or
 
(first day of intake of AZD7648 after C1D1+28) +1 day if AZD7648 is off on C1D1+28-1 day
 
Combinations: (Day 1 of associated anticancer agent for C2 or C1D1 + 28) +1 day; if associated anticancer agent stopped.
 
or
 
(first day of intake of associated anticancer agent C1D1+28) +1 day; if associated anticancer agent and off on C1D1+28-1 day.

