4 ANALYSIS METHODS

4.1 General principles

The below mentioned general principles will be followed throughout the study:

- The planned arm and the actual arm for each patient will be assessed by study medical monitor and provided in a separate MS Excel sheet, which will be used for study summaries. This Excel file will be filed in the TMF at the end of the study.
- Unscheduled assessments will not be included in aggregate summaries and will be listed only. The assessments which are not included in the aggregate summary will be flagged in the listing. Unscheduled assessments will be included in the patient level figures.
- Descriptive statistics will be used for all variables, as appropriate. Continuous variables will be summarised by the number of observations, mean, standard deviation, median, upper and lower quartiles (as applicable), minimum, and maximum. For log transformed data it is more appropriate to present geometric mean, coefficient of variation (CV), median, minimum and maximum. Categorical variables will be summarised by frequency counts and percentages for each category.
- Descriptive statistics will only be presented if $n \geq 3$. If no patients have data at a given time point, then only $n = 0$ will be presented. If data are available for less than 3 participants, no summary statistics other than minimum, maximum and number of observations will be presented
- Unless otherwise stated, percentages will be calculated out of the analysis set total and for modules (core, combination 1 module)/ parts (Part A: dose escalation, Part B: expansion cohorts)/doses.
- For continuous data the mean and median will be rounded to 1 additional decimal place compared to the original data. The standard deviation will be rounded to 2 additional decimal places compared to the original data. Minimum and maximum will be displayed with the same accuracy as the original data.
- For categorical data, percentages will be rounded to 1 decimal place.

- SAS® version 9.4 or higher will be used for all analyses.
- It is acceptable to present large numerical values in more appropriate units. For example, an AUC value of 123,000 ng·h/mL may be reported as 123 µg·h/mL instead of 123,000 ng·h/mL. It is, however, important to keep the units consistent within the report and the precision consistent with that prior to conversion.

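### The SAP ends the on-treatment window for the laboratory worst-value shift tables at an undefined biopsy day, which most Part A patients are not required to have

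*SAP*

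**What the plan says.** SAP 3.2.1.7 sets the window for the reference-range shift tables: "shift tables will present movements from baseline to worst value on-treatment (defined from start of treatment to biopsy day"). The next sentence promises CTCAE grade changes from baseline to on-treatment and gives no window of its own. The same section also says "Maximum post-baseline CTC grade will also be calculated", with no biopsy limit.

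SAP 3.1 has two general rules for extreme values. For maxima and minima, "the maximum/minimum value recorded on treatment will be used (regardless of where it falls in an interval"). A later note says that "in summaries of extreme values, all post baseline values collected are used including those collected at unscheduled visits". Neither mentions a biopsy. SAP 4.1 adds that "Unscheduled assessments will not be included in aggregate summaries and will be listed only"; that governs which values enter a table, not when the window closes.

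SAP 1.2 limits the plan to Part A of the Core Module and of the PLD combination ("Combination Module 1: AZD7648 + PLD. Part A, dose escalation").

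Biopsy timing comes from the protocol. For the Core Module: "Serial biopsies will be collected during screening, on treatment (any time in Cycle 1 between Day 3 and Day 8 [or Y"], and again on progression. For Combination Module 1 Part A: "Serial biopsies will be collected during screening, on treatment (any time in Cycle 1 between Days 3 and Visit Y", and again on progression. Both footnotes encourage fresh biopsies in Part A. They make them mandatory only for PD expansion cohorts or a PD subgroup of an efficacy expansion cohort. Protocol 8.6.3 calls them optional outside a PD expansion cohort, allows the on-treatment timing to be refined, and does not treat a failed biopsy as a deviation.

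**The concern.** Laboratory data are one of the primary endpoint variables, and the shift table is where each patient's worst low, normal or high movement is reported. Its window closes on a procedure that need not occur. None of the approximately 46 Core and 30 Combination Module 1 patients planned for dose escalation is required to have a fresh biopsy by virtue of being in dose escalation.

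Without a biopsy, the programmer must invent an end date. With serial biopsies, the programmer must choose one, and the choice decides whether the table covers a few days or nearly the whole treatment period. Two outputs in the same SAP section could then show different worst values for the same patient. An abnormality that counts as a treatment-emergent adverse event could be absent from the shift table.

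**Working it through.** No sample size, power or error rate depends on this point. The check takes each reading of biopsy day in turn and counts scheduled draws.

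**Inputs**
- Draws after the Cycle 0 Day 1 baseline, from the laboratory rows of protocol Table 1 and Table 13 (Part A): Cycle 1 Days 1, 8, 15 and 22, plus Visit Y on intermittent schedules; Cycle 2 Days 1 and 15; Day 1 of each later cycle.
- Day 8 may be omitted when Visit Y is within 2 days of it (protocol footnotes).
- SAP Table 4 gives windows for Y = 3 and Y = 7 only.
- Horizons shown: one cycle, and six cycles (the maximum number of PLD cycles).

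**Assumptions**
- A draw on the biopsy day counts as inside the window.
- On an intermittent schedule the biopsy falls on or before Visit Y.

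**Totals**
- Continuous: 4 draws in Cycle 1; 4 + 2 (Cycle 2) + 4 (Cycles 3 to 6) = 10.
- Intermittent, Day 8 drawn: 5 and 11.
- Intermittent, Day 8 omitted: 4 and 10.

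**Reading 1: no biopsy.** There is no end date, so the window cannot be derived.

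**Reading 2: screening biopsy.** The end precedes the start, so the window is empty. This is unlikely to be intended.

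**Reading 3: progression biopsy.** Few visits are lost, but only patients who have that biopsy get an end date.

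**Reading 4: Cycle 1 biopsy.** Proportion lost = (total draws − draws kept) / total draws.

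| Schedule and biopsy day | Kept | Lost, 1 cycle | Lost, 6 cycles |
|---|---|---|---|
| Continuous, Day 3 to 7 | Day 1 | 3/4 = 75% | 9/10 = 90% |
| Continuous, Day 8 | Days 1, 8 | 2/4 = 50% | 8/10 = 80% |
| Intermittent, Y = 3, biopsy on Y | Day 1, Y | 3/5 = 60% | 9/11 = 82% |
| Intermittent, Y = 7, Day 8 drawn, biopsy before Y | Day 1 | 4/5 = 80% | 10/11 = 91% |
| Intermittent, Y = 7, Day 8 drawn, biopsy on Y | Day 1, Y | 3/5 = 60% | 9/11 = 82% |
| Intermittent, Y = 7, Day 8 omitted, biopsy before Y | Day 1 | 3/4 = 75% | 9/10 = 90% |
| Intermittent, Y = 7, Day 8 omitted, biopsy on Y | Day 1, Y | 2/4 = 50% | 8/10 = 80% |

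Under this reading at least 50% of Cycle 1 draws and 80% of draws through Cycle 6 are lost on either schedule. Day 15 and Day 22 always go. Both lie inside the DLT assessment period, which runs to Cycle 1 Day 28 (protocol 6.1.3).

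**Against the SAP's other rules.** The note in SAP 3.1 that uses all post-baseline values conflicts with any on-treatment limit. The other SAP 3.1 rule allows an on-treatment limit but sets no biopsy end. These two rules already disagree with each other, whatever SAP 3.2.1.7 says. Maximum post-baseline CTC grade is a separate derivation, so the lack of a cut there is a mismatch between outputs rather than a contradiction.

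**The case against.** The best case against is that little rests on this table. All laboratory results are listed. Maximum post-baseline CTC grade, by-visit summaries, the liver plots and the spaghetti plots are not cut. Safety analysis is descriptive (SAP 4.2.1). DLTs are those documented by the Safety Review Committee (SAP 3.2.1.3), which reviews laboratory abnormalities directly. Development has been halted and an abbreviated CSR is planned. Table specifications sit in a separate document (SAP 1.1), and SAP 4.2.1 defers to the sponsor's output standards, so a working definition may exist there. All of this stands and it limits the severity. It does not make the SAP's stated end date derivable.

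A reader might infer that the plan discards 80% or more of the laboratory safety data. The documents do not support that: the percentages need the Cycle 1 reading, which the SAP never states, and they count visits. Nor do they show that toxicity would be hidden or that a dose decision would change.

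Smaller losses on an intermittent schedule (2/5 = 40% and 8/11 = 73%) would need a biopsy on or after both Visit Y and Day 8. With Y = 3 or 7, the Combination Module 1 footnote excludes this. The Core footnote gives Y as the alternative to Day 8, so it reaches those figures only if an intermittent patient is biopsied on Day 8.

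**Conclusion.** The rule is wrong as written, with low-to-moderate severity. The end date does not exist for patients without a biopsy and is ambiguous for patients with more than one. That conclusion rests on the text alone.

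The size is conditional. If the Cycle 1 biopsy is meant, on a continuous schedule 2 to 3 of 4 scheduled Cycle 1 draws fall outside the window, or 8 to 9 of 10 through Cycle 6. On an intermittent schedule with Y = 3 or 7 and the biopsy by Y, at least 50% and 80% do. If the progression biopsy is meant, few are lost. The documents do not give the number of patients without a biopsy, or the abnormalities that would be missed.

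The effect is confined to the reference-range shift tables and, through the shared on-treatment term, probably the CTCAE grade-change table. An on-treatment limit as such is not the fault.

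**What to change.** Replace biopsy day in SAP 3.2.1.7 with an end date that every treated patient has. The window would run from first dose on Cycle 0 Day 1 through the 28-day safety follow-up visit as windowed in SAP Table 4 (IP discontinuation + 28 ± 7 days), or to data cut-off or death if earlier. Taking the upper edge of that window (28 + 7 = 35 days after IP discontinuation) gives an end date even when the visit is missed. A hard cut at last dose plus 28 days would match the adverse event window but could drop draws that Table 4 assigns to the follow-up visit.

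Apply the same window to the CTCAE grade-change shift table, and keep the SAP 4.1 restriction to data collected before intra-patient dose escalation.

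The new window still departs from the all-post-baseline note in SAP 3.1. Reconcile that note with the on-treatment rule in the same section, so that one stated rule governs worst-value summaries.

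The cost is a phrase in 3.2.1.7, a consistency edit in 3.1 and one programming window. No new data are needed.
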